#### 7.4 Grading and Attribution

##### 7.4.1 Intensity

The study site will grade the intensity of adverse events experienced by study participant according to the criteria set forth in the National Cancer Institute's Common Terminology Criteria for Adverse Events (CTCAE) Version 4.0. This document provides a common language to describe levels of severity, to analyze and interpret data, and to articulate the clinical significance of all adverse events. Adverse events will be graded on a scale from 1 to 5 according to the following standards in the NCI CTCAE manual:

Grade 1 = mild adverse event

Grade 2 = moderate adverse event

Grade 3 = severe and undesirable adverse event

Grade 4 = life threatening or disabling adverse event

Grade 5 = death

All adverse events will be reported and graded whether they are or are not related to disease progression or treatment.

NOTE: A distinction should be drawn between serious and severe AEs. The term "severe" is used to describe the intensity (severity) of a specific event (as in mild, moderate, or severe pain); the event itself, however, may be of relatively minor medical significance (such as severe headache), and does not necessarily need to be considered serious. The term "serious" is used to describe an event based on an event outcome or actions usually associated with events that pose a threat to a patient's life or functioning. Seriousness (not severity) serves as a guide for defining regulatory reporting obligations.

##### 7.4.2 Definition of Attribution

The relationship, or attribution, of an adverse event to an investigational product will be determined by the site investigator. The site investigator will also record the determination of attribution on the appropriate CRF and/or SAE report form. The relationship of an adverse event to the study treatment will be defined as noted below.

##### Unrelated Category:

1 Unrelated: The adverse event is clearly not related to the investigational agent.

##### Related Categories:

2 Unlikely: The adverse event is doubtfully related to the investigational agent.

3 Possible: The adverse event may be related to the investigational agent.

4 Probably: The adverse event is likely related to the investigational agent.

5 Definite: The adverse event is clearly related to the investigational agent.

NOTE: Relationship to study medication will be assessed for the two treatments (GABA and GAD-alum) separately

#### 7.5 Timelines and reporting of SAE

Reporting timelines are necessary to establish compliance with Regulatory Authority requirements for the reporting of drug safety data

The investigator should complete an SAE report and submit via e-mail or fax to the IRB and Diamyd Medical (or its designee) within 24 hours of the investigator becoming aware of an SAE. Any new information relating to an SAE that subsequently becomes available should also be faxed to Diamyd Medical within 24 hours of the investigator becoming aware of the information.

All SAEs must be reported, whether or not considered attributable to the study drug on a separate SAE Report Form according to the following procedures:

As much information as possible should be supplied at the time of the initial report with at least the following information:

- patient, treatment, and trial identifiers
- investigator's name and address
- a description of the event, action taken, and outcome
- the date of onset and current status
- any suspect (study) drug, with its start date, dose and form of administration
- the reason why it is regarded as serious
- the current assessment/opinion of 'causality'
- any other available diagnostic information which will assist the understanding of the event
- if applicable, whether or not the randomization code has been broken for the SAE

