### 5.8 Blinding and Code Breaking

Investigator site staff, persons performing assessments, and data analysts will remain blind to the identity of the treatment from the time of randomization until database lock, using the following methods. (1) randomization data are kept strictly confidential until the time of un-blinding and will not be accessible by anyone else involved in the study, with the exception of the independent, un-blinded pharmacist approving the randomization scheme and providing unblinded safety data to the DSMB per request. (2) the identity of treatment will be concealed by the use of matching placebo to the study drugs that are identical in packaging, labeling, and appearance and scheduled administration. Participants will be blinded in the same manner from randomization until their 12 month research visit. At that time, they will be un-blinded to their GABA treatment by the means of a sealed letter from the research pharmacist. This is done so that those who have received active GABA can continue their treatment, if they so choose, by purchasing GABA over the counter and not potentially losing beta cells as a result of discontinued therapy until results are available (2018/2019). It also allows those who have received placebo to not feel obligated to purchase GABA over the counter since we do not feel there would be benefit after 12 months of placebo therapy. The GAD status will remain blinded throughout the study for all participants. The participants and their families are asked to keep the letter in strictest confidence by not discussing with any study or clinic staff, and present or potential participants to the study.

The treatment code may be broken on an individual basis, in case of an SAE for which the investigator must know the study agent identity to initiate appropriate treatment. The investigator will be supplied the necessary information to break the study blind on an individual patient basis. If the code is broken for one individual subject, the date, time, and reason for un-blinding, together with the investigators signature, must be recorded and the sponsor and Diamyd, or its designee must be notified within 24 hours. Patients will continue in the study unless it is deemed inappropriate.

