#### 6.6 Withdrawal of Participant Consent and Discontinuation of Study Drug:

Study participation may be discontinued for any of the following reasons:

- a. Subject decision to withdraw consent for study
- b. Evidence of allergy to administered products
- c. Intolerable adverse event as judged by study investigator and participant

If the PI chooses to remove the participant from study dosing, rationale will be provided to the participant. If the study drug is discontinued, unless the subject withdraws consent, the subject will be followed for the full treatment period and all data will be collected as scheduled. Attempt will be made to schedule an early end of study assessment in the case of study drug discontinuation. If more than one participant have the same SAE that are thought to be related to treatment compound, the PI and Co-Investigators will meet to discuss whether or not a change in protocol is called for. This information will also be assessed by the independent safety monitoring board. This decision would be reported to the IRB.

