#### 7.7 *Safety Monitoring Board:*

An independent data safety monitoring board (DSMB) who is unaffiliated with the protocol and with no conflict of interest will be appointed. During the course of the study, the independent safety monitoring board will review cumulative study data twice per year to evaluate safety, study conduct and integrity of the trial. At each visit, vital signs, adverse events/side effects, concomitant medications, and pertinent lab values will be recorded. The independent safety monitoring board may also be requested to review data as needed if stopping criteria are met or if safety issues arise that the Sponsors or Principal Investigator would like the independent safety monitor to address. The independent safety monitoring board will be notified in the case that un-blinding occurs. The independent safety monitoring board will conclude each review with their recommendation to the sponsors as to whether the study should continue without change, be modified, or terminated. The sponsor will submit the written recommendations of the independent safety monitoring board to the IRB upon receipt.

The independent data safety monitoring board consisting of [name], UAB Department of Medicine, [name], CRNP, Children's of Alabama, [name], Children's of Alabama, and [name], PhD, Department of Molecular and Clinical Medicine, Sahlgrenska University Hospital, Gothenborg, Sweden, will review data after the 6 months visit to assess benefit of the study. The board may suspend the study at any time if felt needed to evaluate safety further.

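### The 24-hour SAE distribution in section 7.5 omits the DSMB, so a first non-fatal related SAE with the code unbroken may not reach the board until its next half-yearly review

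*Combined protocol and SAP*

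**What the plan says.** **Fast reporting.** Section 7.5 requires the investigator to complete an SAE report and "submit via e-mail or fax to the IRB and Diamyd Medical (or its designee) within 24 hours" of becoming aware of the event. New information on a reported SAE "should also be faxed to Diamyd Medical within 24 hours of the investigator becoming aware of the information". All SAEs are covered, whatever their attribution. The DSMB is not named in either instruction.

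**The board's role.** Under section 7.7 the board "will review cumulative study data twice per year to evaluate safety, study conduct and integrity of the trial". The same section allows it to halt the trial whenever it thinks safety needs closer evaluation. Section 7.8 has two stopping rules: a death related to study medication, and a request from the board. Section 5.8 has the unblinded pharmacist "providing unblinded safety data to the DSMB per request".

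**Other ways the board may hear of an event.**
- Section 7.7: the board "may also be requested to review data as needed if stopping criteria are met or if safety issues arise" that the sponsors or the principal investigator want examined.
- Section 7.7: "The independent safety monitoring board will be notified in the case that un-blinding occurs".
- Section 6.6: when two or more children have the same SAE thought to be treatment-related, "the PI and Co-Investigators will meet to discuss whether or not a change in protocol is called for", and the board assesses the information too.

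**The concern.** The protocol relies on the board for any safety-driven stop short of a related death, but its written rule for rapid SAE reporting leaves the board out. A power to halt the trial at any time is of little use for an event the board has not been told about. Access to unblinded data on request has the same limit: the board must already know that there is something to ask about.

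The design makes timing matter. Both injections are given by Month 1 and oral dosing is daily for 12 months, so much of a child's exposure can fall between two scheduled reviews. In that interval the decision to involve the board rests mainly with people who are blinded to allocation.

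**Working it through.** No sample-size or error-rate calculation is involved. The check sets the sections side by side and derives one interval.

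**Step 1: who is told, and how fast.**

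| Trigger | Recipient | Time limit | Section |
|---|---|---|---|
| Any SAE, initial report | IRB, Diamyd Medical | 24 hours | 7.5 |
| New information on an SAE | Diamyd Medical | 24 hours | 7.5 |
| Individual code break | Sponsor, Diamyd Medical | 24 hours | 5.8 |
| Un-blinding | DSMB | none stated | 7.7 |
| Same related SAE in at least 2 children | DSMB (assesses) | none stated | 6.6 |
| Stopping criteria met, or a request by sponsors or PI | DSMB (may be asked) | none stated | 7.7 |
| Scheduled review | DSMB | twice a year | 7.7 |

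Every row with a 24-hour limit omits the DSMB, and every row that reaches the DSMB lacks a deadline or depends on the calendar.

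**Step 2: apply the routes to one case.** Take a first, non-fatal SAE judged related, with the code unbroken.
- The un-blinding notice does not apply, because no code was broken.
- The section 6.6 rule does not apply, because it needs a second child with the same event.
- The related-death rule in section 7.8 does not apply, because the event is not fatal.
- Ad hoc review is possible, but only if the sponsors or the principal investigator choose to ask.
- The scheduled review is the only certain route.

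**Step 3: the wait for a scheduled review.** The one input is the stated frequency of two reviews a year.
- Interval if evenly spaced: 12 months / 2 = 6 months. This is the longest wait, for an event just after a review.
- Mean wait if events fall uniformly in the interval: 6 / 2 = 3 months.

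The comparison is with 24 hours for the IRB and Diamyd Medical. Even spacing is an assumption. The protocol fixes no interval, so 6 months is not a guaranteed ceiling. Section 7.7 also mentions a board review after a 6-month visit, but its stated purpose is to assess benefit and no SAE triggers it.

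**Step 4: what this means for one child.** A child randomised just after a review has the second injection at about Month 1. That is about 6 - 1 = 5 months before the next evenly spaced review, by which time the child is halfway through the 12 months of oral dosing.

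**The case against.** The case against is substantial, and parts of it stand.

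- **The ad hoc route is broad.** It needs neither matching events nor a visible difference between arms. At a single site, an unusual number of SAEs can be noticed in pooled data, and the board can then ask the pharmacist for unblinded data. A reader might infer that a cluster of different SAEs in one arm would trigger nothing. The documents do not support that. This route could catch such a cluster, but it is discretionary and has no deadline.
- **The board is not alone in seeing allocations.** Under section 5.8 the investigator can break an individual code for an SAE. SUSARs are unblinded where required, and Diamyd Medical and Janssen/JDRF can be given what they need to unblind individual cases for regulatory reporting. It would therefore be wrong to say that only the board has access to unblinded data. These are single cases, however, and the documents give none of these parties an arm-level safety summary. An unblinded SUSAR should also reach the board through the notice in section 7.7, though no time is set.
- **The worst single event is covered.** A related death is itself a stopping rule in section 7.8.
- **The attribution filter is loose.** Section 7.4.2 places even unlikely events among the related categories, so the section 6.6 rule may capture more than it first appears to. It still needs a second child with the same event.
- **The sponsors can act too.** The board's recommendations go to them.

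These points narrow the gap to a first, non-fatal related SAE without a code break and without a request for review. They do not close it.

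**Conclusion.** The point holds in this limited form. The routing rule in section 7.5 leaves out the DSMB, and the other routes are conditional and untimed. A first, non-fatal related SAE with the code unbroken may therefore not come to the board until its next scheduled review: up to about 6 months, mean about 3, if reviews are evenly spaced and events uniformly timed. This delay is a possibility, not a certainty, because an ad hoc request could shorten it.

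It is a gap in a design choice, not a contradiction in the text, and it is worth closing because closing it costs almost nothing. A reader might want to turn the delay into a number of extra children treated. The documents do not support that: they give no recruitment period, no expected SAE rate and no threshold for halting, and such a count would presume that the board stops enrolment on receiving the report.

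**What to change.** In section 7.5, name the DSMB as a recipient of initial SAE reports and follow-up information, in blinded form and within the same 24 hours. This should cover at least SAEs judged related. The text should say which of the section 7.4.2 categories count as related for this purpose, since that scale includes unlikely events; sending all SAEs would avoid the question.

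Then align the other sections:
- Section 5.8: include the DSMB in the notice after a code break, so that it matches section 7.7.
- Section 6.6: give a time limit for passing repeated related SAEs to the board.
- Section 7.7: refer to the section 7.5 distribution and state the intended spacing of the half-yearly reviews.

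On receiving a blinded report, the board can use its existing right to request unblinded data from the pharmacist. An automatic SAE count by arm with each report should not be added. One arm's count would rise by one each time and so reveal that child's allocation, and section 7.7 places board members at the trial's own institutions.

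The cost is a short amendment, a few more e-mails and a small reading load for the board. Blinded reports leave site blinding as it is, and sample size, power and alpha do not change.

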#### 7.6 *Pregnancy*

Pregnant and breast feeding women are excluded from the study. Menarchal females must have a negative urine pregnancy test prior to randomization and a negative urine pregnancy test at each visit with GAD-alum/placebo administration. Participants and their partners will be strongly advised to avoid pregnancy for one year following the last dose of GAD-alum/placebo and instructed to use adequate form of birth control. A pregnancy occurring during the study must be recorded on the Pregnancy Report Form and no further doses with GAD-alum/placebo will be administered. If a pregnancy is verified the Pregnancy Report Form must be sent to Diamyd within 24 hours of site being aware and a copy of the report must remain on-site in the chart and followed until delivery.

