## COHORTS

### 5.3 Inclusion Criteria

- Males and Females 4-18 years of age.
- Be positive for autoantibody GAD-65. If not collected. Collect and send at visit 1.
- They must meet the ADA criteria for diabetes : classic symptoms, plus blood sugar >200mg/dL or fasting blood sugar >126mg/dL
- Enrolled within 4 weeks of diagnosis (+ 1 week window)
- If the participant is female and post-menarchal two forms of contraception must be used during the study if not abstinent. The types of contraception deemed acceptable would be oral contraceptive pills, intrauterine devices and barrier methods.
- Signed informed consent form

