### 5.4 Exclusion Criteria

- Chronic systemic steroid use, including inhaled compounds, or any medication which can alter glucose metabolism
- Treated with any other oral or injectable hyperglycemic medication other than insulin.
- Obesity, defined as BMI >95 percentile, or BMI >27 in adolescents with acanthosis score between 1-1.5
- Pregnant and/or breastfeeding
- History of seizure disorder (epilepsy, head trauma, cerebral vascular accident), or any clinical features of continuous motor unit activity in proximal muscles
- Patients on medications which may disturb GABA action, such as Baclofen, Valium, Acamprosate, Neurontin, or Lyrica
- History of alcoholism or any substance abuse
- Chronic disease (such as liver, cancer, cystic fibrosis, or renal failure)
- Chromosome abnormality (such as trisomy 21, Turner Syndrome,..etc)
- History of anemia, or significantly abnormal hemoglobin results at screening
- Clinically significant history of acute reaction to vaccines and other drugs in the past.
- Known history of HIV or hepatitis
- Unwillingness to comply with conditions of the protocol
- History of illness, besides diabetes within 2 weeks of first GAD-alum/placebo injection
- Any condition that the PI feels would not be beneficial for the subject to be on study.

5.5 *Informed Consent:*

Potential participants will be approached by research personnel during initial hospitalization for new onset Type I Diabetes at The Children’s Hospital of Alabama to provide information regarding the study. If interested, the informed consent document will be provided to the potential participant and contact information will be provided for study personnel. Subjects choosing to participate will be asked to consent for study participation prior to, or at the first clinic visit post diagnosis. Before the first follow up clinic appointment at one month, written consent from the parents and patient 14 years or older, or assent from children aged 7-13, will be obtained in a quiet setting prior to the initiation of any study procedures. Patients will not be consented in writing until they are able to demonstrate adequate understanding of all aspects of the study and consent process. A copy of the consent form will be given to the patient. The signed consent form remains in the patients study files at the clinical center. Consented participants will then be randomized

5.6 *Randomization:*

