**Table 1. Randomization and study visits**

Study	Day 1 Baseline Randomization	Mo 1	Mo 5	Mo 8	Mo 12
	Visit 1 <5 weeks from diagnosis	Visit 2 ± 7	Visit 3 ± 7	Visit 4 ± 7	Visit 5 ± 7
Group 1 GABA-GAD group (GABA+GAD-alum)  30 subjects	GABA twice daily, every day from Baseline to Month 12				
	Prime injection GAD-alum 20 µg	Boost injection GAD-alum 20 µg			
Group 2  GABA group ( GABA+ Placebo GAD-alum)  43 subjects	GABA twice daily, every day from Baseline to Month 12				
	Prime injection Placebo GAD-alum	Boost injection Placebo GAD- alum			
Group 3  Placebo group (Placebo GABA + Placebo GAD-alum)  37 subjects	Placebo GABA twice daily, every day from Baseline to Month 12				
	Prime injection Placebo GAD-alum	Boost injection Placebo GAD- alum			

5.7 *Treatment Doses and Schedule*

- 1) Oral Gamma-Aminobutyric Acid (GABA)

We shall not exceed the recommended adult dosages (up to 1.5 grams/day) and we will adjust the dose to the body surface area of the children enrolled in our study. For example, the average adult has a body surface area of 1.5 - 2 m^2. Therefore, the current recommended adult dosage is equivalent to 1 grams/m^2/day, and this is the dose we will be giving to our trial participants. This total daily amount will be divided in two daily doses to be given with breakfast and dinner. The GABA will be supplied by the manufacturer NOW Foods in 200 mg capsules. Each dose will be rounded to the nearest 100 mg. The placebo will also be provided by NOW Foods and will be indistinguishable in appearance, taste, and smell from the GABA capsules. The capsules will be opened and dissolved in water, or sprinkled on food immediately before consumption. Documentation of these products by site personnel will be documented in the case report form (CRF).

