**Table 2 Schedule of Patient Visits, Visit Windows and Study Drug Administration**

Study	Intervention				
	Day 1 Baseline	Month 1	Month 5	Month 8	Month 12
	Visit 1	Visit 2 ± 7	Visit 3 ± 7	Visit 4 ± 7	Visit 5 ± 7
GABA/ Placebo	Every day from Day 1 through Month 12				
GAD-alum/ Placebo	Prime: One injection	Boost: One injection			

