### 6.2 Study Events

The treatment therapy consists of oral GABA or placebo given with meals twice daily at breakfast and dinner throughout the study and 2 GAD-alum or placebo injections given at baseline and 1 month later . i.e.1 prime and 1 booster dose.

Study visits for all patients will occur for randomization at baseline and subsequently for the injection, and for medical monitoring.

General assessments include:

- medical history and routine physical exam
- concomitant medications
- adverse events
- Laboratory Assessments (hematology, biochemistry, urine pregnancy test as appropriate, islet antibodies, liver function and urine studies)

Metabolic assessments include:

- Glucose records and reports of hypoglycemia
- Insulin Dose
- HbA1c
- Mixed Meal Tolerance Test

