**Table 3. Schedule of Study Events**

	At Baseline	1mo post baseline (+/- 1 week)	5mo post baseline (+/- 1 week)	8mo post baseline (+/-1 week)	12mo postbaseline (+/- 1week)
Informed Consent	X (or before)				
Randomization	X				
Gad-alum or placebo injection a	X	X			
Oral GABA or placebo administration starts	X				
Medical History	X				

Vital Signs	X	X	X	X	X
Ht	X	X	X	X	X
Weight	X	X	X	X	X
Physical Exam + Neurological	X	X	X	X	X
Hgb A1C	Done as standard of care at every visit.		Obtain results from chart		
Growth Rate	X	X	X	X	X
Hx of DKA	X	X	X	X	X
Autoimmune antibodies	Done as standard of care at diagnosis. Obtain and document results.		X		X
Mixed Meal Tolerance Test ( glucose, glucagon, C peptide, )	X	X (only fasting and 90 min samples)	X (only fasting and 90 min samples)		X
CBC with diff	X		X		X
Hx of Hypoglycemia	X	X	X	X	X
Complete Metabolic Profile	X		X		X
Glucagon( fasting), glucose, C-peptide	X	X	X		X
Urine Pregnancy test (for menstruating females)	X	X	X	X	X
Total Daily Insulin Dose( U/kg)	X	X	X	X	X
Medication Review/ Concomitant Medications	X	X	X	X	X
Cell Activation Markers	X		X		X
Inflammatory Cytokines	X		X		X
Skin exam: injection site: b	X	X	Ask regarding any issues after last injection. X		
Urinalysis (if available) for microalbuminuria and creatinine and C-peptide	X	X	X	X	X
Adverse Events	X	X	X	X	X
Proinsulin	X		X		X

a GAD-alum/Placebo administration: The target date for the second GAD-alum/Placebo administration will be set in accordance with baseline (i.e. the first injection, Visit 1) so that the second dose will be 1 month post first dose.

b Inspection of injection site before and 60 minutes after injection by investigator or nurse

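### Section 7.6 requires only GAD-alum/placebo to stop in an on-study pregnancy and gives no instruction for oral GABA/placebo, which is dosed daily to Month 12

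*Combined protocol and SAP*

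**What the plan says.** The trial gives two investigational products. Sections 5.7 and 6.2 and Tables 1 and 2 schedule GAD-alum/placebo as two injections, at Day 1 and Month 1. Oral dosing is set out in Table 1 as "GABA twice daily, every day from Baseline to Month 12", with placebo on the same schedule, and in Table 2 as "Every day from Day 1 through Month 12".

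Pregnancy is handled in these places:

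- Section 5.4 lists "Pregnant and/or breastfeeding" among the exclusions, and section 7.6 opens with "Pregnant and breast feeding women are excluded from the study".
- Section 5.3 sets a contraception condition: "If the participant is female and post-menarchal two forms of contraception must be used during the study if not abstinent".
- Table 3 and section 6.7 schedule a urine test at all five visits for girls who menstruate. Section 7.6 demands a negative result before randomization and at the injection visits.
- For a pregnancy that arises on study, section 7.6 states: "A pregnancy occurring during the study must be recorded on the Pregnancy Report Form and no further doses with GAD-alum/placebo will be administered". A verified pregnancy is reported within 24 hours and followed to delivery.

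Section 6.6 allows the PI to take a participant off study dosing, with reasons given. Unless consent is withdrawn, she stays in follow-up and her data are still collected. The three listed reasons for ending participation are withdrawn consent, allergy and an intolerable adverse event; pregnancy is not among them.

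**The concern.** The only dosing action required in an on-study pregnancy applies to the product that is finished after the first month. The product taken every day for a year is not mentioned. The test schedule makes this visible: the protocol looks for pregnancy at Months 5 and 8 but attaches no required drug action to a positive result at those visits.

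At stake is the safety of an adolescent participant and her pregnancy. The protocol requires contraception throughout the study, so it treats pregnancy during oral dosing as something to prevent, yet it does not say what happens to the oral drug if prevention fails. Nothing here bears on sample size, power or type I error.

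**Working it through.** No published figure needs reproducing. The check sets the stop rule in 7.6 against the dosing schedule (5.7, 6.2, Tables 1 and 2) and the pregnancy tests (Table 3, 6.7).

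**Inputs.** Injections at Day 1 and Month 1. Oral dosing from Day 1 to Month 12. Urine tests at baseline and Months 1, 5, 8 and 12. Planned arm sizes 30 (GABA + GAD-alum), 43 (GABA + placebo injection) and 37 (all placebo).

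**Step 1: when the rule has a dose to stop.** The last injection is at Month 1, so the required stop has nothing to act on for 12 − 1 = 11 of the 12 dosing months.

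**Step 2: each post-baseline test.** Oral dosing left = 12 − visit month.

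| Positive test at | Injection still due | Oral dosing left (months) | Drug stop required by 7.6 |
|---|---|---|---|
| Month 1 | yes | 12 − 1 = 11 | second injection only |
| Month 5 | no | 12 − 5 = 7 | none |
| Month 8 | no | 12 − 8 = 4 | none |
| Month 12 | no | 12 − 12 = 0 | none |

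Three of the four post-baseline tests (Months 1, 5 and 8) fall while oral dosing has months to run. At none of them is the oral product required to stop.

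**Step 3: which active drug the rule can reach.** In the GABA-only arm (43 planned) both injections are placebo, so the rule can never stop that arm's active drug. Active oral GABA is planned for 30 + 43 = 73 of 110 participants. Staff are blinded (5.8), so the response cannot routinely be adapted to the arm.

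**Step 4: whether another section supplies the missing stop.** Section 6.6 gives permission, at the PI's choice. Section 5.4 governs entry. No other section gives an instruction on oral dosing in pregnancy.

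**Limits of the arithmetic.** The figures use nominal months and ignore the ±7-day windows. Section 6.1 postpones an injection while a patient is febrile, without a stated limit; a late second injection would shorten the 11 months.

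**The case against.** The strongest reply is that the PI can already stop the oral drug under 6.6, and at a single site one PI would probably do so. That stands as far as it goes: stopping is available. But 6.6 only permits, and the protocol chose to make the injection stop mandatory; it gives no reason to treat the daily product differently.

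A second reply is that the opening sentence of 7.6, "Pregnant and breast feeding women are excluded from the study", may cover removal of anyone who becomes pregnant. The wording is not expressly limited to entry, so some ambiguity remains. The more natural reading is that it repeats 5.4, because a rule stopping only the injections would be unnecessary if the participant had to leave. The protocol does repeat itself elsewhere, so this argument is not conclusive; ambiguity also calls for a clarifying clause.

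Third, there are other safeguards: contraception, testing at every visit, prompt reporting, follow-up to delivery, classification of a birth defect as a serious adverse event (7.2), and twice-yearly safety board review (7.7). These prevent, detect or report. None says what to do with the oral drug.

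Fourth, the introduction describes GABA as generally safe, and section 5.7 limits the dose to recommended adult levels. Neither statement addresses pregnancy.

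A reader might go further and infer that two pregnant participants would be managed differently. The documents do not support that: there is one site, and the decision lies with its PI.

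**Conclusion.** The gap is real and should be closed. As written, section 7.6 requires no drug stop for a pregnancy found at Month 5 or Month 8, with 7 or 4 months of oral dosing left. At Month 1 it withholds one injection and leaves 11 months of oral dosing without a required stop. Stopping the oral product is permitted throughout and required at no point.

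Three stronger inferences should be avoided. First, the documents do not show that GABA harms a pregnancy; they do not show that it is safe either. Second, they do not show that a pregnant participant would in fact be kept on drug: the PI may stop it, and the consent pages were removed, so any instruction given there cannot be checked. Third, the 11 of 12 months describes when the injection rule has no dose left to act on. It is not anyone's exposure in pregnancy and does not measure risk.

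The number affected is probably small, but the documents give neither the number of post-menarchal girls nor an expected number of pregnancies. The primary analysis is unaffected. The conclusion rests on the nominal schedule and on reading the opening sentence of 7.6 as an entry condition.

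**What to change.** Amend 7.6 in two steps:

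1. A positive urine test at any visit holds both GAD-alum/placebo and oral GABA/placebo until pregnancy is verified or ruled out.
2. A verified pregnancy permanently discontinues both.

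The two steps matter because 7.6 already separates out a verified pregnancy for reporting, and a single unconfirmed urine result should not end treatment. State that scheduled follow-up continues off drug under 6.6 and that the participant is analysed by intention to treat under 9.0. Leave the list of reasons in 6.6 unchanged, because it concerns ending participation.

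One practical detail: section 6.2.1 gives the oral product just before the test meal, so at those visits the urine result should be read first. A participant on hold would do the meal test without that dose.

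The cost is a sentence or two in 7.6. No visit or test is added and the analysis plan does not change. The downside is that at most a few participants come off oral drug, and they remain in follow-up.
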